7.2.3.2 Events of Clinical Interest

Selected non-serious and serious adverse events are also known as Events of Clinical Interest (ECI) and must be recorded as such on the Adverse Event case report forms/worksheets and reported within 24 hours to the Sponsor and within 2 working days to Merck Global Safety. (Attn: Worldwide Product Safety; [contact])

Events of clinical interest for this trial include:

1. An overdose of Merck product, as defined in Section 7.2.1 - Definition of an Overdose for This Protocol and Reporting of Overdose to the Sponsor, that is not associated with clinical symptoms or abnormal laboratory results.
2. An elevated AST or ALT lab value that is greater than or equal to 3X the upper limit of normal and an elevated total bilirubin lab value that is greater than or equal to 2X the upper limit of normal and, at the same time, an alkaline phosphatase lab value that is less than 2X the upper limit of normal, as determined by way of protocol-specified laboratory testing or unscheduled laboratory testing.*

*Note: These criteria are based upon available regulatory guidance documents. The purpose of the criteria is to specify a threshold of abnormal hepatic tests that may require an additional evaluation for an underlying etiology. The trial site guidance for assessment and follow up of these criteria can be found in the Investigator Trial File Binder (or equivalent).

3. In the event a subject develops any of the following AEs, a detailed narrative of the event should be reported as an ECI to the Sponsor within 24 hours and to Merck Global Safety within 2 working days of the event:

- a. Grade \geq 3 diarrhea
- b. Grade \geq 3 colitis
- c. Grade \geq 2 pneumonitis
- d. Grade \geq 3 hypo- or hyperthyroidism

A separate guidance document has been provided entitled “event of Clinical Interest and Immune-Related Adverse Event Guidance Document.” This document provides guidance regarding identification, evaluation and management of ECIs and irAEs. Additional ECIs are identified in this guidance document and also need to be reported to the Sponsor within 24 hours and to Merck Global Safety within 2 working days of the event.

Subjects should be assessed for possible ECIs prior to each dose. Lab results should be evaluated and subjects should be asked for signs and symptoms suggestive of an immune-related event. Subjects who develop an ECI thought to be immune-related should have additional testing to rule out other etiologic causes. If lab results or symptoms indicate a possible immune-related ECI, then additional testing should be performed to rule out other etiologic causes. If no other cause is found, then it is assumed to be immune-related.

ECIs that occur in any subject from the date of first dose through 90 days following cessation of treatment, or the initiation of a new anticancer therapy, whichever is earlier, whether or not related to the Merck’s product, must be reported within 24 hours to the Sponsor and to Merck Global Safety within 2 working days.

7.2.4 Evaluating Adverse Events

An investigator who is a qualified physician will evaluate all adverse events according to the NCI Common Terminology for Adverse Events (CTCAE), version 4.0. Any adverse event which changes CTCAE grade over the course of a given episode will have each change of grade recorded on the adverse event case report forms/worksheets.

All adverse events regardless of CTCAE grade must also be evaluated for seriousness.

Table 10 Evaluating Adverse Events

An investigator who is a qualified physician, will evaluate all adverse events as to:

V4.0 CTCAE Grading	Grade 1	Mild; asymptomatic or mild symptoms; clinical or diagnostic observations only; intervention not indicated.
	Grade 2	Moderate; minimal, local or noninvasive intervention indicated; limiting age-appropriate instrumental ADL.
	Grade 3	Severe or medically significant but not immediately life-threatening; hospitalization or prolongation or hospitalization indicated; disabling; limiting self-care ADL.
	Grade 4	Life threatening consequences; urgent intervention indicated.
	Grade 5	Death related to AE
Seriousness	A serious adverse event is any adverse event occurring at any dose or during any use of Merck product that:	
	† Results in death ; or	
	† Is life threatening ; or places the subject, in the view of the investigator, at immediate risk of death from the event as it occurred (Note: This does not include an adverse event that, had it occurred in a more severe form, might have caused death.); or	
	† Results in a persistent or significant disability/incapacity (substantial disruption of one’s ability to conduct normal life functions); or	
	† Results in or prolongs an existing inpatient hospitalization (hospitalization is defined as an inpatient admission, regardless of length of stay, even if the hospitalization is a precautionary measure for continued observation. (Note: Hospitalization [including hospitalization for an elective procedure] for a preexisting condition which has not worsened does not constitute a serious adverse event.); or	
	† Is a congenital anomaly/birth defect (in offspring of subject taking the product regardless of time to diagnosis); or	
	Is a new cancer ; (that is not a condition of the study) or	
	Is an overdose (whether accidental or intentional). Any adverse event associated with an overdose is considered a serious adverse event. An overdose that is not associated with an adverse event is considered a non-serious event of clinical interest and must be reported within 24 hours.	
	Other important medical events that may not result in death, not be life threatening, or not require hospitalization may be considered a serious adverse event when, based upon appropriate medical judgment, the event may jeopardize the subject and may require medical or surgical intervention to prevent one of the outcomes listed previously (designated above by a †).	
Duration	Record the start and stop dates of the adverse event. If less than 1 day, indicate the appropriate length of time and units	
Action taken	Did the adverse event cause the Merck product to be discontinued?	
Relationship to test drug	Did the Merck product cause the adverse event? The determination of the likelihood that the Merck product caused the adverse event will be provided by an investigator who is a qualified physician. The investigator’s signed/dated initials on the source document or worksheet that supports the causality noted on the AE form, ensures that a medically qualified assessment of causality was done. This initialed document must be retained for the required regulatory time frame. The criteria below are intended as reference guidelines to assist the investigator in assessing the likelihood of a relationship between the test drug and the adverse event based upon the available information. The following components are to be used to assess the relationship between the Merck product and the AE ; the greater the correlation with the components and their respective elements (in number and/or intensity), the more likely the Merck product caused the adverse event (AE):	
	Exposure	Is there evidence that the subject was actually exposed to the Merck product such as: reliable history, acceptable compliance assessment (pill count, diary, etc.), expected pharmacologic effect, or measurement of drug/metabolite in bodily specimen?
	Time Course	Did the AE follow in a reasonable temporal sequence from administration of the Merck product? Is the time of onset of the AE compatible with a drug-induced effect (applies to trials with investigational medicinal product)?
	Likely Cause	Is the AE not reasonably explained by another etiology such as underlying disease, other drug(s)/vaccine(s), or other host or environmental factors

Relationship to Merck product (continued)	The following components are to be used to assess the relationship between the test drug and the AE: (continued)	
	Dechallenge	
Was the Merck product discontinued or dose/exposure/frequency reduced? If yes, did the AE resolve or improve? If no, this is a positive dechallenge. If no, this is a negative dechallenge. (Note: This criterion is not applicable if: (1) the AE resulted in death or permanent disability; (2) the AE resolved/improved despite continuation of the Merck product; or (3) the trial is a single-dose drug trial); or (4) Merck product(s) is/are only used one time.)

	Rechallenge	
Was the subject re-exposed to the Merck product in this study? If yes, did the AE recur or worsen? If yes, this is a positive rechallenge. If no, this is a negative rechallenge. (Note: This criterion is not applicable if: (1) the initial AE resulted in death or permanent disability, or (2) the trial is a single-dose drug trial); or (3) Merck product(s) is/are used only one time). NOTE: IF A RECHALLENGE IS PLANNED FOR AN ADVERSE EVENT WHICH WAS SERIOUS AND WHICH MAY HAVE BEEN CAUSED BY THE MERCK PRODUCT, OR IF REEXPOSURE TO THE MERCK PRODUCT POSES ADDITIONAL POTENTIAL SIGNIFICANT RISK TO THE SUBJECT, THEN THE RECHALLENGE MUST BE APPROVED IN ADVANCE BY THE U.S. CLINICAL MONITOR AS PER DOSE MODIFICATION GUIDELINES IN THE PROTOCOL.

	Consistency with Trial Treatment Profile	
Is the clinical/pathological presentation of the AE consistent with previous knowledge regarding the Merck product or drug class pharmacology or toxicology?

The assessment of relationship will be reported on the case report forms /worksheets by an investigator who is a qualified physician according to his/her best clinical judgment, including consideration of the above elements.
		
Record one of the following	Use the following scale of criteria as guidance (not all criteria must be present to be indicative of a Merck product relationship).	
Yes, there is a reasonable possibility of Merck product relationship.	
There is evidence of exposure to the Merck product. The temporal sequence of the AE onset relative to the administration of the Merck product is reasonable. The AE is more likely explained by the Merck product than by another cause.
	
No, there is not a reasonable possibility Merck product relationship	
Subject did not receive the Merck product OR temporal sequence of the AE onset relative to administration of the Merck product is not reasonable OR there is another obvious cause of the AE. (Also entered for a subject with overdose without an associated AE.)
	

7.2.5 Sponsor Responsibility for Reporting Adverse Events

All Adverse Events will be reported to regulatory authorities, IRB/IECs and investigators in accordance with all applicable global laws and regulations.

8.0 CHEMOTHERAPY

Part A LS-SCLC:

All patients will receive chemotherapy with either cisplatin and etoposide or carboplatin and etoposide. All patients should receive four cycles of chemotherapy, given over 3 weeks each, unless there is evidence of disease progression or patient intolerance. Cisplatin and etoposide is the preferred regimen; for patients unable to tolerate cisplatin in the opinion of the treating clinician, carboplatin/etoposide is an acceptable alternative.

8.1 Drug Supply and Storage

Cisplatin, carboplatin, and etoposide are standard, commercially available drugs. Investigators will use commercially available supplies and will store drug as per the instructions provided in the package insert. This section does not apply to induction chemotherapy given prior to trial enrolment.

8.2 Drug Administration

8.2.1 Etoposide

During cycles 1-4, etoposide 100 mg/m² IV will be administered over approximately 4 hours on days 1, 2, and 3 of each 3 week cycle. BSA will be obtained by the Mosteller equation:

$$BSA = ((ht(cm) * wt(kg)) / 3600)^{1/2}$$

Etoposide will be given for up to 4 cycles.

8.2.2 Cisplatin

During cycles 1-4 of the induction phase, subjects for whom cisplatin/etoposide has been selected as chemotherapy will receive cisplatin IV at a dose of 80 mg/m² on day 1 of each 3 week cycle. The dosage will be administered over approximately 2 hours. BSA will be obtained by the Mosteller equation. Cisplatin will be given for up to four cycles.

Pre-hydration and post-hydration can be administered per institutional standards.

8.2.3 Carboplatin

During cycles 1-4 of the induction phase, subjects for whom carboplatin/etoposide has been selected as chemotherapy will receive carboplatin IV at AUC 5 on day 1 of each 3 week cycle.

The dosage will be administered over approximately 30 minutes. AUC should be calculated using the Calvert formula. Carboplatin will be given for up to four cycles.

Creatinine clearance must be calculated prior to every dose of carboplatin using the Cockcroft-Gault formula for estimating creatinine clearance in mL/min based on serum creatinine:

$$\text{Men: } \frac{[(140 - \text{Age (yrs)}) * \text{weight (kg)}]}{[72 * \text{serum creatinine (mg/dL)}]}$$

$$\text{Women: } \frac{[(140 - \text{Age (yrs)}) * \text{weight (kg)}]}{[72 * \text{serum creatinine (mg/dL)}]} * 0.85$$

If calculated GFR is greater than 125 mL/min, the maximum GFR used to calculate carboplatin dose should be 125 mL/min to avoid potential toxicity due to overdosing.

8.2.4 Cisplatin Versus Carboplatin

Cisplatin is the preferred platinum agent. For patients unable to tolerate cisplatin in the opinion of the treating clinician, carboplatin is an acceptable alternative. Subjects are allowed to switch from cisplatin to carboplatin during therapy, if the subject becomes ineligible for further cisplatin therapy in the opinion of the treating clinician, and the clinician feels that switching to carboplatin is in the best interest of the subject

8.3 Dose Delays and Dose Modifications for Cytotoxic Chemotherapy

8.3.1 Dose Delays

Drug related toxicities must be resolved to baseline or \leq grade 1 (with the exception of alopecia and grade 2 fatigue) prior to administering the next dose. Subjects should not receive the next cycle of chemotherapy if any of the following apply:

- Absolute neutrophil count (ANC) $< 1500/\text{mm}^3$
- Platelet count $< 100,000/\text{mm}^3$
- Hemoglobin $< 9 \text{ g/dL}$
- Total bilirubin > 2.5 times the upper limit of normal (ULN)
- AST and ALT > 2.5 times ULN, or > 5 times ULN if liver metastases are present
- Inadequate renal function defined as creatinine clearance $< 45 \text{ mL/min}$ by the standard Cockcroft and Gault formula
- Additionally, treatment may be delayed due to any other reasons as per the treating physician's discretion.

Chemotherapy treatment may be delayed up to 21 days.

8.3.2 Dose Modifications

Dose modifications for carboplatin, cisplatin, and etoposide will follow local guidelines. Suggestions for dose reductions are provided below.

	Etoposide Dose	Cisplatin Dose	Carboplatin Dose
Starting Dose	100 mg/m ²	80 mg/m ²	AUC 5
Dose Level -1	75 mg/m ²	60 mg/m ²	AUC 4
Dose Level -2	50 mg/m ²	40 mg/m ²	AUC 3

8.3.2.1 Suggested Dose Modifications for Hematologic Toxicity

Drug Related Toxicity	Etoposide	Cisplatin	Carboplatin
Febrile Neutropenia (temperature $\geq 38.5^{\circ}\text{C}$ and ANC $< 1000/\text{m}^3$)	Decrease 1 dose level	Decrease 1 dose level	Decrease 1 dose level
Platelets $< 25,000/\text{m}^3$	Decrease 1 dose level	Decrease 1 dose level	Decrease 1 dose level
Grade 4 anemia (Hgb < 6.5 g/dL)	Decrease 1 dose level	Decrease 1 dose level	Decrease 1 dose level

8.3.2.3 Suggested Dose Modifications for Non-Hematologic Toxicity

For all toxicity \leq grade 2 (except neuropathy), the dose level for all drugs should be maintained. All dose modifications should be made based on the worst grade toxicity seen.

Drug Related Toxicity	Etoposide	Cisplatin	Carboplatin
Nausea/Vomiting \geq Grade 3 despite optimal medical treatment	Decrease 1 dose level	Decrease 1 dose level	Decrease 1 dose level

Diarrhea \geq Grade 3 despite optimal medical treatment	Decrease 1 dose level	Decrease 1 dose level	Decrease 1 dose level
Neuropathy, grade 2 lasting > 7 days or grade 3	No modification	Decrease 2 dose levels	No modification
Neuropathy grade 4	No modification	Discontinue	No modification
Total bilirubin >2 x ULN	50% of previous dose	No modification	No modification
Total bilirubin >5 x ULN	Discontinue	No modification	No modification
Other grade \geq 3 toxicities (except fatigue and arthralgia/myalgia)	Decrease 1 dose level	Decrease 1 dose level	Decrease 1 dose level

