5.0 METHODOLOGY

5.1 Entry Criteria

5.1.1 Diagnosis/Condition for Entry into the Trial

5.1.2 Subject Inclusion Criteria

In order to be eligible for participation in this trial, the subject must:

1. Be willing and able to provide written informed consent/assent for the trial.
2. Be ≥ 18 years of age on day of signing informed consent.
3. Modified for clarification as some patient with induction therapy could have no measurable disease. Have a performance status of 0 or 1 or 2 on the ECOG Performance Scale.
4. Demonstrate adequate organ function as defined below; all screening labs should be performed within 10 days of treatment initiation.

Table 1 Adequate Organ Function Laboratory Values

System	Laboratory Value
Hematological	
Absolute neutrophil count (ANC)	≥1,500 /mcL
Platelets	≥100,000 / mcL
Hemoglobin	≥9 g/dL or ≥5.6 mmol/L
Renal	
Serum creatinine OR Measured or calculated ^a creatinine clearance (GFR can also be used in place of creatinine or CrCl)	≤1.5 X upper limit of normal (ULN) OR ≥60 mL/min for subject with creatinine levels > 1.5 X institutional ULN
Hepatic	
Serum total bilirubin	≤ 1.5 X ULN OR Direct bilirubin ≤ ULN for subjects with total bilirubin levels > 1.5 ULN
AST (SGOT) and ALT (SGPT)	≤ 2.5 X ULN OR ≤ 5 X ULN for subjects with liver metastases
Coagulation	
International Normalized Ratio (INR) or Prothrombin Time (PT)	≤1.5 X ULN unless subject is receiving anticoagulant therapy as long as PT or PTT is within therapeutic range of intended use of anticoagulants
Activated Partial Thromboplastin Time (aPTT)	≤1.5 X ULN unless subject is receiving anticoagulant therapy as long as PT or PTT is within therapeutic range of intended use of anticoagulants
^a Creatinine clearance should be calculated per institutional standard.	

5. Female subject of childbearing potential should have a negative urine or serum pregnancy within 2 weeks of study entry. If the urine test is positive or cannot be confirmed as negative, a serum pregnancy test will be required.
6. Female subjects of childbearing potential should be willing to use 2 methods of birth control or be surgically sterile, or abstain from heterosexual activity for the course of the study through 120 days after the last dose of study medication (Reference Section 5.7.2). Subjects of childbearing potential are those who have not been surgically sterilized or have not been free from menses for > 1 year.

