3.5 Hepatic

The following AE terms, if considered \geq Grade 2 or greater (or any grade with dose modification or use of systemic steroids to treat the AE), are considered ECIs and should be reported to the Sponsor within 24 hours of the event:

- Autoimmune hepatitis
- Hepatitis
- Transaminase elevations

All attempts should be made to rule out other causes such as metastatic disease, infection or other hepatic diseases. However the AE should be reported regardless of etiology.

Drug Induced Liver Injury (DILI)

In addition, the event must be reported as a Drug Induced Liver Injury (DILI) ECI, if the patient meets the laboratory criteria for potential DILI defined as:

- An elevated alanine transaminase (ALT) or aspartate transaminase (AST) lab value that is greater than or equal to three times (3X) the upper limit of normal (ULN) and
- An elevated total bilirubin lab value that is greater than or equal to two times (2X) ULN and
- At the same time, an alkaline phosphatase (ALP) lab value that is less than 2X ULN,
- As a result of within-protocol-specific testing or unscheduled testing.

Note that any hepatic immune ECI meeting DILI criteria should only be reported once as a DILI event.

Course of Action

Grade 2 events:

- Report as ECI
- Hold pembrolizumab when AST or ALT >3.0 to 5.0 times ULN and/or total bilirubin >1.5 to 3.0 times ULN.
- Monitor liver function tests more frequently until returned to baseline values (consider weekly).
 - Treat with 0.5-1 mg/kg/day methylprednisolone or oral equivalent and when LFT returns to grade 1 or baseline, taper steroids over at least 1 month, consider prophylactic antibiotics for opportunistic infections, and resume pembrolizumab per protocol
- Permanently discontinue for inability to reduce corticosteroid dose to 10 mg or less of prednisone or equivalent per day within 12 weeks.
- Permanently discontinue pembrolizumab for patients with liver metastasis who begin treatment with Grade 2 elevation of AST or ALT, and AST or ALT increases $\geq 50\%$ relative to baseline and lasts ≥ 1 week.

Grade 3 events:

- Report as ECI
- Discontinue pembrolizumab when AST or ALT >5.0 times ULN and/or total bilirubin >3.0 times ULN.
- Consider appropriate consultation and liver biopsy to establish etiology of hepatic injury, if necessary

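### For a worst bilirubin above 2 and up to 3 x ULN, section 8.3.2.3 gives Part A patients two different etoposide doses, and one entry route in Table 1 admits patients whom section 8.3.1 bars from the next cycle

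*Combined protocol and SAP*

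**What the plan says.** Four places in the combined protocol and SAP bear on this.

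- **Section 8.3.2.3, lead sentence.** For toxicity of grade 2 or lower, "the dose level for all drugs should be maintained". Neuropathy is the only exception named. The next sentence adds: "All dose modifications should be made based on the worst grade toxicity seen".
- **Section 8.3.2.3, table.** The row "Total bilirubin >2 x ULN" gives, for etoposide, "50% of previous dose", and leaves cisplatin and carboplatin unchanged. A further row stops etoposide above 5 x ULN. Neither row carries a grade.
- **Section 8.3.1.** Drug-related toxicity has to return to baseline or to grade 1 or lower before the next dose, except alopecia and grade 2 fatigue. A list of findings then rules out the next cycle, among them "Total bilirubin > 2.5 times the upper limit of normal (ULN". Chemotherapy may be delayed by at most 21 days.
- **Section 5.1.2, Table 1.** The main entry limit for total bilirubin is 1.5 x ULN. The alternative is "Direct bilirubin ≤ ULN for subjects with total bilirubin levels > 1.5 ULN", with no upper cap on the total.

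The grade bands come from Appendix 13.4, section 3.5 Hepatic. Under grade 2 events it says "Hold pembrolizumab when AST or ALT >3.0 to 5.0 times ULN and/or total bilirubin >1.5 to 3.0 times ULN". Its grade 3 entry starts above 3.0 x ULN.

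**The concern.** Within 8.3.2.3, the lead sentence depends on grade and the bilirubin row on a multiple of ULN. If the row begins inside the grade 2 band, the same patient is told both to keep the etoposide dose and to halve it. Separately, if entry allows a total bilirubin that 8.3.1 treats as a bar to chemotherapy, a patient can be admitted to a chemoradiation part and then be unable to receive the chemotherapy that defines it.

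What is at stake is a patient's etoposide exposure and the clarity of the Part A safety data. Section 9.2.3 tabulates adverse events by dose and cohort of MK-3475. If clinicians resolve the conflict differently, the chemotherapy background of those tables varies for reasons unrelated to the study drug.

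**Working it through.** The plan states no figure to reproduce. The check applies each rule to the same bilirubin value.

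**Step 1. Lay the rules side by side.** Grade bands are from Appendix 13.4, 3.5; the other columns are from 8.3.2.3 and 8.3.1.

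| Worst total bilirubin (x ULN) | Grade | Lead sentence, 8.3.2.3 | Etoposide row, 8.3.2.3 | Over the 2.5 x ULN bar, 8.3.1 |
|---|---|---|---|---|
| up to 1.5 | 1 or lower | keep dose | none | no |
| above 1.5 to 2.0 | 2 | keep dose | none | no |
| above 2.0 to 2.5 | 2 | keep dose | half | no |
| above 2.5 to 3.0 | 2 | keep dose | half | yes |
| above 3.0 to 5.0 | 3 or higher | does not apply | half | yes |
| above 5.0 | 3 or higher | does not apply | stop | yes |

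The lead sentence and the row disagree in the third and fourth lines only, that is above 2 and up to 3 x ULN.

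**Step 2. Size of the disagreement.** Section 8.2.1 gives etoposide 100 mg/m² on three days per cycle.

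- Dose kept: 3 x 100 = 300 mg/m² per cycle.
- Dose halved: 3 x 50 = 150 mg/m² per cycle.

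**Step 3. When it takes effect.** While a drug-related rise is still at grade 2, 8.3.1 holds the next dose on either reading. Once it has resolved, 8.3.2.3 sets the dose from the worst grade seen, and the two lines then part.

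**Step 4. Position relative to the DLT window.** Section 9.1 limits DLT assessment to 22 days from the start of therapy. Cycles last 3 weeks (section 8.0). If chemotherapy cycle 1 starts on day 1 and the bilirubin rise occurs on study, cycle 2 is due on day 1 + 21 = 22, and later if held under 8.3.1. The disputed dose is therefore given at or after the end of the window.

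**Step 5. Entry against the bar.**

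- Main route: total at most 1.5 x ULN. Since 1.5 < 2.5, nobody entering this way is above the bar at entry.
- Alternative route: total above 1.5 x ULN with direct bilirubin within ULN. Any total above 2.5 x ULN satisfies this criterion and is also over the bar. The list in 8.3.1 makes no exception for baseline value or direct fraction, so a stable value stays barred.

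**Step 6. How many patients.** The documents give no frequency for bilirubin above 2 and up to 3 x ULN. Taking 1% to 5% of Part A purely as an assumption, 40 x 0.01 = 0.4 to 40 x 0.05 = 2 patients would be expected. The textual conflict does not depend on this.

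**The case against.** The strongest reply is that little turns on the wording. Section 8.3.2 says that local guidelines govern and that its reductions are suggestions, and 8.3.2.3 is itself headed as suggested. A reader would normally let the specific bilirubin row prevail over a general sentence. The advisory status stands and limits the weight of the point. The specific-over-general reading is plausible but not secure. The neuropathy row also reaches into grade 2, and there an exception was written; the bilirubin row is the only other one that does, and it has none.

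Four stronger readings are tempting, and the documents do not support them.

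- *Treatment at the time of the rise depends on which line is read (full etoposide, half or no cycle).* For a drug-related rise to grade 2 the cycle waits on any reading, by the opening rule of 8.3.1. Only the dose after recovery is open.
- *Dose-finding is affected.* Step 4 places the disputed dose at or beyond the edge of the DLT window, so it hardly bears on whether a patient counts as DLT-free.
- *The limits of 2, 2.5 and 5 x ULN contradict one another.* They can be applied in sequence. The conflict is with the lead sentence.
- *Eligibility in general admits patients over the bar.* Only the direct-bilirubin route does so. It matters only in Part A, because Part B has no on-study chemotherapy.

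It is also fair to say that entry criteria and chemotherapy hold rules serve different purposes and need not share one limit. That is accepted. The gap is that 8.3.1 does not address a patient whom Table 1 knowingly allows in.

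**Conclusion.** The point holds as a minor, specific inconsistency. For a worst total bilirubin above 2 and up to 3 x ULN, 8.3.2.3 supports both an unchanged and a halved etoposide dose after recovery, a twofold difference per cycle from the starting dose. This rests on reading the bilirubin range listed under grade 2 in Appendix 13.4 as the grade 2 band; no outside source is used.

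The entry mismatch also holds, but only for a Part A patient with total bilirubin above 2.5 x ULN and direct bilirubin within ULN.

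The consequences are confined to individual chemotherapy dosing and to the interpretation of later Part A safety data. Escalation decisions, sample size, endpoints and the planned analyses are not affected, given the timing assumptions in step 4.

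**What to change.** Two reconciliations are needed.

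1. In 8.3.2.3, make the lead sentence and the bilirubin rows agree, given the grade bands in Appendix 13.4, section 3.5.
2. For Part A, reconcile the bilirubin bar in 8.3.1 with the direct-bilirubin allowance in Table 1, so that the text says what happens to a patient admitted by that route with a total above 2.5 x ULN.

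Which limit and which action apply is for the sponsor's clinicians to decide. The cost is a few words, with no added procedures or patients. One caution: Table 1 serves both parts, so an edit there should be worded so that it does not change Part B eligibility by accident.
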